4.6.2 Additional Safety Assessments

4.6.2.1 Clinical Laboratory Evaluation

The baseline value will be the last non-missing value taken prior to first dose of study drug.

Quantitative values evaluated by the central or local laboratory including hematology, serum chemistry, additional serum chemistry (includes complement panel, cytokine panel, and bile acids), coagulation, and urinalysis will be summarized using mean, standard deviation,

minimum, maximum and median by treatment group at each analysis visit. Additionally, a within-participant change will be calculated as the post-baseline measurement minus the baseline measurement and summarized in the same way. Each laboratory result will be classified as low (L), normal (N), or high (H) at each visit according to the laboratory supplied reference ranges.

Central lab results should be summarized if they're available at an analysis visit. If both local and central laboratory results are available at an analysis visit, the central lab values should be used preferentially for analysis. If only local labs are available at an analysis visit but central lab values are missing, then local labs may be used for analysis.

The number and percentage of participants below and above the reference range will be summarized for each dose level and overall at each visit.

Frequency tabulations of qualitative clinical laboratory variables (urinalysis) will be presented for each treatment group at each visit.

Selected laboratory abnormalities will be evaluated based on pre-specified threshold level (potentially clinically significant [PCS]) criteria. If both the baseline and on-treatment values of a parameter are beyond the same threshold limit for that parameter, then the on-treatment value will be considered a PCS value only if it is more extreme (farther from the limit) than was the baseline value. If the baseline value for a parameter is missing and the on-treatment value of a parameter is beyond the PCS limit, then the on-treatment value will be considered a PCS value. The pre-defined criteria for PCS laboratory values are presented below.

Table 4 Potentially Clinically Significant Laboratory Values

Pre-specified Threshold Values for Selected Laboratory Tests (Potentially Clinically Significant Laboratory Criteria)	
Laboratory Parameter	Pre-Specified Level
Chemistry	
Sodium	<132 mEq/L
Potassium	<3.0, <3.5, >5.0, >6.0 mEq/L
Serum bicarbonate	<10, <12, >30, >32 mEq/L
Creatinine	>25% increase from baseline
CK	>25% increase from baseline
ALT	>25% increase from baseline or 5 x ULN
AST	>25% increase from baseline or 5 x ULN
Glucose	>250 mg/dL
Troponin T and troponin I	>25% increase from baseline
Hematology	
Hemoglobin	<9 g/dL
Hematocrit	<27%

For each laboratory threshold criterion, the number and percent of participants who have a laboratory value meeting the threshold criteria during the investigational period will be summarized by dose level group and visit.

Laboratory results will be graded using NCI-CTCAE v4.03 or higher, where possible. NCI-CTCAE grade of laboratory evaluations will be summarized by number and percentage of participants at each visit.

The number and percentage of participants with \geq Grade 1 shift from baseline in laboratory test result will be summarized by dose level and laboratory parameter.

The following data may be presented graphically by treatment group:

- Laboratory test results using box plot (by visits within each period),
- Change from baseline in laboratory test results using box plot (by visits within each period),
- Laboratory test results using spaghetti plot.

All laboratory results will be listed. Laboratory results that are above or below normal limits will be flagged, along with clinical significance, in the listings. In addition, laboratory results that meet or exceed the pre-specified levels (i.e., are above [or below as appropriate] the pre-specified levels as shown in the above [table](#)) will be flagged.

Should local laboratory values be collected, they will be listed and out of range values will be flagged.

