^f Day 2 and Day 3 vital signs to be collected every 12 hours (±30 minutes), prior to discharge, and daily after discharge.

^g ECHOs should include an assessment of pulmonary hypertension as well as structural and functional abnormalities. Particular attention should be paid to ECG and ECHO abnormalities specific to myocarditis. Refer to [Section 4.6.1](#) for management of ECG and ECHO results and the role of the site pediatric cardiologist.

- ^h See [Appendix 1](#) for list of laboratory assessments.
- ⁱ It is recommended to use the central laboratory to analyze laboratory tests that are drawn prior to dosing, and after the Week 16 Visit and to use the local laboratory to analyze laboratory tests that are drawn at Baseline, Dosing, Days 1, 2, and Weeks 1 through 16. However, the local laboratory can be used for other visits if needed (for example, the local laboratory can accommodate the analysis with a smaller amount of blood) or if the local laboratory does not accommodate the appropriate analysis, the central laboratory may be used.
- ^j See [Section 4.6.1](#) for details related to the evaluation of cardiac enzymes; monitoring, diagnosis, and treatment of myocarditis; and the role of the site pediatric cardiologist.
- ^k See [Section 4.6.2](#) for details related to the monitoring, diagnosis, and treatment of hepatobiliary toxicity and the role of the site hepatologist.
- ^l LFTs, CK (including CK isoenzymes), C-reactive protein, and serum bicarbonate only.
- ^m Cytokine panel: Following Week 4 cytokine panel collection, in cases of clinically important elevated bilirubin, elevated aminotransferases, elevated troponins, and/or elevated creatine phosphokinase that in the Investigator's judgment may be related to T-cell responses, repeat cytokine panel testing is suggested. Appropriate care for an individual subject will be determined by the Investigator based on an assessment of the subject's overall medical status.
- ⁿ Complement panel: Following Week 4 complement panel collection, in cases of clinically important elevated bilirubin, elevated aminotransferases, ascites, thrombocytopenia, acute renal insufficiency, and/or anemia that in the Investigator's judgment may be related to complement activation, repeat complement panel testing is suggested. Appropriate care for an individual subject will be determined by the Investigator based on an assessment of the subject's overall medical status.

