Visit Window (days)	-1	±3	±3	±3	+10	±3	±14	±14	±14	±14	±14	±14
Diary of ventilator dependence ^{a,b}	X											
Ventilator Dependence Questionnaire ^b						X		X	X	X	X	X
Contact subject's caregiver ^c						X						
Physical examination ^d			X		X		X	X	X	X	X	X
Vital signs ^e			X		X		X	X	X	X	X	X
12-Lead ECG ^f			X		X		X	X	X		X	X
ECHO ^f			X				X		X		X ^g	X ^g
Growth parameters			X		X		X	X	X	X	X	X
Tanner stage (puberty assessment)							X		X		X ^{ff}	
Samples for:												
Safety labs (hematology) (central lab) ^{h,i}							X	X	X		X	X
Safety labs (hematology) (local lab) ^{h,i}			X		X							
Safety labs (chemistry) (central lab) ^{h,i,j,k,l}							X	X	X		X	X
Safety labs (chemistry) (local lab) ^{h,i,j,k}		X ^m	X	X ^m	X							
Cytokine panel (central lab) ^{h,n}		As clinically indicated										
Complement panel (central lab) ^{h,o}		As clinically indicated										
Troponin T and/or I (central lab) ^{h,j}							X	X	X		X	X
Troponin T and/or I (local lab) ^{h,j}		X	X	X	X							

Study Phase/Visit	Daily	Weeks 9, 10, 11	Week 12	Weeks 13, 14, 15	Week 16	Weeks 20, 28, 32, 40, 44	Week 24	Week 36	Week 48 or Early Withdrawal	Month 15	Months 18, 24, 30, 36, 42	Months 48, 54, 60
Study Day(s)	NA	63, 70, 77	84	91, 98, 105	112	140, 196, 224, 280, 308	168	252	336	456	548, 730, 913, 1095, 1278	1460, 1643, 1825
Visit Window (days)	-1	±3	±3	±3	+10	±3	±14	±14	±14	±14	±14	±14
Coagulation parameters (central lab) ^{h,i}							X	X	X		X	X
Anti-AAV8 NAb and TAb (central lab)			X		X		X	X	X		X	X
Anti-MTM1 antibody (central lab)			X		X		X	X	X		X	X
IFN-γ ELISpot (PBMCs) (central lab)		As clinically indicated ^p										
HLA typing (central lab) ^q			X ^q						X ^q		X ^q	
Urinalysis (central lab) ^{h,i}							X	X	X		X	X
Urinalysis (local lab) ^{h,i}		X	X		X							
Serum bile acid assay (fasting preferred; central lab)			X				X	X	X	X	X	X
Liver ultrasound ^k			X		X		X	X	X		X	X
Bone age (wrist X-ray) (not applicable for Germany)			X				X		X		X ^{ee}	
Assessment of ventilator parameters			X		X		X		X		X ^{ff}	
MIP, MEP, P0.1, tidal volume ^r			X		X		X		X		X ^{ff}	
Ventilator Weaning and Discontinuation Assessment			X ^s		X ^s		X ^s		X ^s		X ^{s, ff}	
Daytime polysomnogram							X		X ^t			
Secretions management assessment ^u			X		X	X	X	X	X		X	X
Motor milestone assessments ^v			X		X		X	X	X	X	X	X
Bayley-III, motor domain ^v			X		X		X	X	X	X	X ^{ff}	
CHOP INTEND ^{v,w}			X		X		X	X	X		X ^{ff}	
MFM-32 ^v			X		X		X	X	X		X ^{ff}	

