Month 36	1095	1005-1186	1005-1186	1005-1186	1005-1186	1005-1186	1005-1186	1005-1186	1005-1186	1005-1186
Month 42	1278	1187-1369	1187-1369	1187-1369	1187-1369	1187-1369	1187-1369	1187-1369	1187-1369	1187-1369
Month 48	1460	1370-1551	1370-1551	1370-1551	1370-1551	1370-1551	1370-1551	1370-1551	1370-1551	1370-1551
Month 54	1643	1552-1734	1552-1734	1552-1734	1552-1734	1552-1734	1552-1734	1552-1734	1552-1734	1552-1734
Month 60	1825	≥1735	≥1735	1735-2007	≥1735	≥1735	1735-2007	≥1735	≥1735	1735-2007
Month 72	2190			2008-2372			2008-2372			2008-2372
Month 84	2555			2373-2737			2373-2737			2373-2737
Month 96	2920			2738-3102			2738-3102			2738-3102
Month 108	3285			3103-3467			3103-3467			3103-3467
Month 120	3650			≥3468			≥3468			≥3468

Abbreviations: NA = Not Applicable.
 Grey area indicates NA.

Table 10 Analysis Visit Windows for Safety Endpoints

Analysis Visits	Scheduled Day in Protocol (Day)	Analysis Windows (Day)												
		(a) LFTs, CK (including CK isoenzymes), CRP, serum bicarbonate (local & central)	(b) Chemistry excluding (a), hematology (local & central)	(c) Urinalysis (local & central)	(d) Cytokine panel, complement panel (central)	(e) Troponin T and/or I (local & central)	(f) Coagulation (local)	(g) Viral Shedding (central)	(h) Serum bile acid (central)	(i) Platelet monitoring	(i) Vital signs	(j) 12-Lead ECG	(k) Liver ultrasound	(l) Anti-AAV8, Anti-MTM1 (central)
Baseline	-1	≤ -1	≤ -1	≤ -1	≤ -1 [#]	≤ -1	≤ -1		≤ -1	≤ -1	≤ 1*	≤ -1	≤ -1	
Dosing	1							1			1*			
Day 2	2	1-4	1-4	1-4		1-4		2		1-4	2	1-4		
Day 3	3				1-5			3-5			3-5			
Wk 1	7	5-10	5-10	5-10	6-10	5-10	1-17	6-14		5-10	6-10	5-10		
Wk 2	14	11-17	11-21	11-21	11-17	11-17				≥11	11-21	11-21		
Wk 3	21	18-24			18-24	18-24		15-28						
Wk 4	28	25-31	22-42	22-42	25-31	25-35	18-42				22-42	22-42	1-56	1-35
Wk 5	35	32-38			32-38			29-42						
Wk 6	42	39-45			39-45	36-49								36-49
Wk 7	49	46-52			46-52			43-56						
Wk 8	56	53-59	43-70	43-59	53-59	50-59	43-112				43-70	43-70		50-70
Wk 9	63	60-66		60-66	60-66	60-66		57-70						
Wk 10	70	67-73		67-73	67-73	67-73								
Wk 11	77	74-80		74-80	74-80	74-80		71-84						
Wk 12	84	81-87	71-98	81-98	81-87	81-87			1-126		71-98	71-98	57-98	71-98
Wk 13	91	88-94			88-94	88-94		85-98						
Wk 14	98	95-101			95-101	95-101								
Wk 15	105	102-108			102-108	102-108		99-136						
Wk 16	112	109-140	99-140	99-140	109-140	109-140					99-140	99-140	99-140	99-140
Wk 24	168	141-210	141-210	141-210	141-210	141-210	113-210	137-210	127-210		141-210	141-210	141-210	141-210

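### After Week 4 the SAP's by-visit cytokine and complement summaries would rest on clinically triggered samples, so later trends and dose contrasts could reflect who was sampled

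*SAP*

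**What the plan says.** **Sampling.** Protocol 5.3.1 takes both panels at screening. Protocol 5.4 adds a cytokine draw at Baseline and schedules both panels at Day 3 and Weeks 1 to 4. From Week 5 both rows read "As clinically indicated", and Protocol 5.5 keeps that entry from Week 9 to Month 60. The footnotes to 5.4 give the triggers. For cytokines: "Following Week 4 cytokine panel collection, in cases of clinically important elevated bilirubin, elevated aminotransferases, elevated troponins" or creatine phosphokinase, where the investigator judges a T-cell response possible. For complement: "Following Week 4 complement panel collection, in cases of clinically important elevated bilirubin, elevated aminotransferases, ascites, thrombocytopenia, acute renal insufficiency" or anemia, where complement activation is thought possible. Repeat testing is suggested, not required. Protocol 4.6.2.3 is to the same effect.

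**Analysis.** SAP 4.6.2.1 names both panels within "additional serum chemistry (includes complement panel, cytokine panel, and bile acids". It asks for mean, standard deviation, "minimum, maximum and median by treatment group at each analysis visit", for within-participant change from baseline in the same form, and for the number and percentage of participants below and above the reference range at each visit by dose. SAP 4.10.2, Table 10, has a column headed "Cytokine panel, complement panel (central" whose windows run to Month 60. Neither section separates scheduled from triggered samples.

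**The concern.** A by-visit table is read as a description of the dose group at that visit. Up to Week 4 that reading is fair for these panels, because every treated child is due a sample. From Week 5 a child contributes only if someone suspected a problem that the panel might explain.

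A reader who moves from the Week 4 row to the Week 5 row would see a change in the mean that may be only a change in which children are in it. The same applies to low dose against high dose. If the doses differ in how often, or for what reason, testing is triggered, the two columns compare differently selected children.

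The SAP reports descriptively and tests nothing, so these tables are themselves the result. Immune-mediated toxicity is an identified risk of the product (Protocol 6.5.2), so the panels are likely to be read with that question in mind.

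**Working it through.** The plan states no figure on this point, so there is none to reproduce. The check sets the schedule against the windows.

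**1. Post-dose windows in Table 10 column (d)**

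| Windows | Count | Scheduled draw in Protocol 5.4/5.5? |
|---|---|---|
| Day 3, Weeks 1 to 4 | 5 | Yes |
| Weeks 5 to 16 | 12 | No |
| Weeks 24, 36, 48 | 3 | No |
| Months 18, 24, 30, 36, 42, 48, 54, 60 | 8 | No |

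Without a scheduled draw: 12 + 3 + 8 = 23. Total: 5 + 23 = 28. Column (d) has no window at Month 15 or at Months 72 to 120.

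**2. Are the windows meant for tables?** SAP 4.10.2 says that data with no planned by-visit table need no windowing. The later windows in column (d) therefore imply planned tables.

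**3. How the same table treats a comparable assay.** Platelet monitoring is scheduled at Baseline, Day 2 and Weeks 1 and 2 (Protocol 5.4). Its Table 10 column ends at Week 2. The SAP version history says the windows were revised in version 4.0 to follow each endpoint's own visit schedule. Column (d) does not.

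**4. Percentages.** SAP 4.1 bases percentages on participants with non-missing data. As pure illustration, suppose only the 5 of 17 high-dose children with related hepatobiliary SAEs (Protocol 1.4.2) were sampled in a window and all were out of range. The table shows 5/5 = 100%. If the other 12 were in range, the share of treated children is 5/17 = 29%. Any low-dose count under the same conditions also shows 100%.

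**5. Visit labels.** A triggered sample on Day 150 is labelled Week 24 (window 141 to 210). If the same child is sampled again on Day 175, the rule in 4.10.2 keeps Day 175 (7 days from Day 168, against 18), whichever value was more abnormal.

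**6. Why no size can be given.** Let *k* of *n* children be affected, with *r* times the unaffected level, and let only affected children be sampled. The full-sample mean is (*kr* + *n* − *k*)/*n*, and the reported mean is *r*. All values of *r* are assumed.

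- *n* = 17, *k* = 5, *r* = 2: 22/17 = 1.29 against 2.00, so 55% too high.
- *n* = 17, *k* = 12, *r* = 2: 29/17 = 1.71 against 2.00, so 17% too high.
- *n* = 17, *k* = 5, *r* = 0.5: 14.5/17 = 0.85 against 0.50, so 41% too low.

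For the dose contrast, suppose there is no true dose difference and take the related-SAE shares in Protocol 1.4.2 as assumed trigger fractions *p* (1/6 low, 8/17 high). With correlation ρ between marker and trigger, the mean among sampled children shifts by ρ·φ(z₁₋ₚ)/*p* standard deviations. For ρ = 0.3, 0.5, 0.7 this is 0.45, 0.75, 1.05 at low dose and 0.25, 0.42, 0.59 at high dose, a spurious high-minus-low difference of −0.20, −0.33, −0.46. A negative ρ reverses the sign. Size and direction follow from the assumptions, not from the documents.

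**The case against.** **The schedule compared may not be the one that generated the data.** SAP 4.0 (April 2024) cites the protocol v11 schedule for its windows. The protocol in hand is v12 (May 2024), and no child was dosed under v10 or later. Most Week 5 to 16 samples would have been taken under versions not available here, which may have scheduled further draws. This stands. It is why the finding is tied to the current schedule and why the fix allows for the version in force for each child.

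**Safeguards exist.** SAP 4.1 reports n, so falling counts will be visible. No between-dose test is planned (SAP 2). Change from baseline is within-participant. Toxicity by dose is covered by the summaries of adverse events of special interest (SAP 4.6.1). This stands in part: the tables will not mislead about how many children had toxicity. But n does not say why those children were sampled, and within-child change does not remove a rise that belongs to the triggering event.

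**The consequence is limited.** Protocol 5.1.1.8 collects these panels in addition to the standard safety laboratory tests. The safety endpoints do not name them, and no efficacy or dose conclusion depends on them. This stands and keeps the point modest.

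**Stronger readings.** A reader might infer that the whole time course and dose contrast describe only sick children. The documents do not support that, because Day 3 and Weeks 1 to 4 are scheduled for everyone. Protocol 1.5 places the onset of bilirubin rises in the four fatal cases at 1 to 4 weeks, and AT132-related thrombocytopenia in the first 2 weeks, so the early course is well covered. A reader might also infer a definite overstatement, such as the 55% above. That rests on an assumed ratio, direction and sampled fraction. The triggers are also wider than serious events: Protocol 1.5 describes troponin and CK rises as common.

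**Conclusion.** The mismatch is real. Under the current schedule, 23 of the 28 post-dose windows for the cytokine and complement panels have no scheduled draw, and the SAP plans by-visit, by-dose summaries in all of them. Summaries from Week 5 to Month 60 would describe children selected for a suspected abnormality, and trends or dose contrasts there could reflect that selection.

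The size and direction of any distortion cannot be derived from the documents. The Day 3 to Week 4 summaries are sound. Bile acids share the SAP phrase but have scheduled draws from Week 12 (Protocol 5.5) and are not affected. The conclusion assumes that the protocol versions under which the samples were taken had the same post-Week-4 rule. Where one did not, its scheduled draws belong in the tables.

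**What to change.** In SAP 4.6.2.1 and Table 10 column (d), for the cytokine and complement panels only:

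- Limit by-visit summaries, change from baseline, reference-range counts and percentages, and any box plots to protocol-scheduled draws. Under the current schedule these are pre-dose, Day 3 and Weeks 1 to 4. If an earlier version scheduled more, use the draws scheduled under the version in force for that child.
- Remove the windows that have no scheduled draw.
- Show later results in the laboratory listing that SAP 4.6.2.1 already requires and in individual (spaghetti) plots, flagged as clinically indicated. Give the trigger and the number of children sampled by dose. If the trigger is not recorded, show the abnormality or adverse event current at the time of sampling.
- While editing the column, state the complement baseline. Table 10 marks its baseline window as applying to cytokines only, although Protocol 5.3.1 collects complement at screening.

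The cost is SAP wording, a flag in the dataset and fewer table rows after Week 4. No result is lost, because all laboratory results remain listed.

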4.6.2.2 Liver Safety Assessment

The liver safety assessments will be summarized by the categories below based on the measurements from Alkaline Phosphatase (ALP), Alanine Transaminase (ALT), Total Bilirubin, Aspartate Transaminase (AST) and their combination. These parameters will be based on measurements from all laboratory (central and local [when units/reference ranges are available]).

The participant's highest value during any post-dose follow-up visit in the following periods will be summarized by period:

- Baseline through Week 24 visit (inclusive)
- >Week 24 through Week 48 visit
- >Week 48 to End of Study visit
- Overall for the study

Table 5 Liver Function Test Thresholds

Liver Test	Criteria
ALT	>3 x ULN
	>5 x ULN
	>10 x ULN
	>20 x ULN
AST	>3 x ULN
	>5 x ULN
	>10 x ULN
	>20 x ULN
Total Bilirubin	>2 x ULN
Direct Bilirubin	>2 x ULN
Serum Bile Acids	>2 x ULN

Liver Test	Criteria
ALP	>1.5 x ULN
ALT and/or AST and Total Bilirubin	(ALT and/or AST > 3 x ULN) and (Total Bilirubin > 2 x ULN)
ALT and Total Bilirubin	(ALT > 3 x ULN) and (Total Bilirubin > 2 x ULN)
ALT and Direct Bilirubin	(ALT > 3 x ULN) and (Direct Bilirubin > 2 x ULN)
ALT and/or AST, Total Bilirubin, and ALP	(ALT and/or AST > 3 x ULN) and (Total Bilirubin > 2 x ULN) and (ALP < 2 x ULN)

Criteria where 2 or more parameters are evaluated will be with the measurements on the same day or up to 1 day apart. The denominator for each criterion will be the number of participants who have at least one value during the 24 week investigational period. The number and percentage of participants meeting the criteria during the 24 week investigational period will be summarized by treatment group. In addition, a by-visit summary showing the number of participants achieving these thresholds will be provided.

Change from baseline in special liver laboratory parameters of interest (eg, bilirubin, AST, ALT, and CK) will be summarized descriptively.

The following data may be presented graphically by treatment group:

- Matrix scatter plot of maximum liver tests values during each period of the study,
- eDISH plot
- Individual display of liver tests for selected participants experiencing potentially clinically significant criteria in liver tests.
- Individual line plots display of selected liver tests in terms of xULN will be provided as described in [Section 4.2.6](#).

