Following the occurrence of fatal serious AEs (SAEs) in Study ATX-MTM-002, the Sponsor, in consultation with the DMC and external experts, evaluated the data and reassessed the benefit/risk profiles of the 1.0×10^{14} vg/kg and 3.0×10^{14} vg/kg dose levels. As of the data cutoff date of 08 July 2020, 5 subjects who received 3.0×10^{14} vg/kg AT132 developed AT132-related SAEs involving the hepatobiliary system. In 2 subjects, these SAEs resolved; in 3 subjects, fatal events occurred subsequent to severe cholestatic liver dysfunction. Within the 3.0×10^{14} vg/kg dose level cohort, 8 of 17 subjects (47.1%) experienced 26 SAEs considered related to AT132. In contrast, within the 6 subjects dosed at the 1.0×10^{14} vg/kg dose level, all of whom are ≥ 2 years from AT132 administration, 1 (16.7%) subject experienced 4 AT132-related SAEs, all resolved, and none involved the hepatobiliary system. In addition to a favorable safety profile observed in the subjects treated with 1.0×10^{14} vg/kg, a clinically meaningful benefit continues to be observed in this group at last follow-up. In this group, which had a mean 20.5 hours (SE 2.02) of ventilation per day at baseline ($n = 5$ [83.3%] with invasive ventilation; $n = 1$ [16.7%] with non-invasive ventilation), 5 out of 6 (83.3%) subjects were ventilatory independent at last follow-up (as of data cutoff date 08 July 2020). With respect to gross motor development, at baseline 5 of the 6 subjects did not perform any of the following major motor milestones: sit unassisted for 30 seconds, raise self to standing position, stand alone, or walk alone. At baseline, 1 subject did sit unassisted for 30 seconds but did not perform the remaining motor tasks. At last follow-up following AT132 administration at 1.0×10^{14} vg/kg, 5 out of 6 subjects performed all of these motor tasks, including walking alone. Regarding performance on the Children's Hospital of Philadelphia Infant Test of Neuromuscular Disorders (CHOP INTEND), this 1.0×10^{14} vg/kg group demonstrated a baseline mean score of 37.7 (SE 2.42). At last follow-up, performance had improved to a mean score of 56.5 (3.97).

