As data from Study ATX-MTM-002 subjects treated at the 1.0×10^{14} vg/kg dose level demonstrate significant and clinically meaningful benefit, an overall benefit/risk analysis by the Sponsor, in consultation with the DMC, had determined the benefit/risk profile of the 1.0×10^{14} vg/kg dose level to be favorable, and superior to the 3.0×10^{14} vg/kg dose level.

Based on feedback from the US FDA, the Sponsor improved the assay for determination of vg titer of manufactured AT132 drug product lots. Following validation, the Sponsor used this 2nd generation assay, with enhanced precision compared to the 1st generation methodology, to recharacterize the vg content of all previously administered drug product lots from Study ATX-MTM-002. This recharacterization analysis demonstrated that the 1.0×10^{14} vg/kg dose level based on the 1st generation titer method equates to 1.3×10^{14} vg/kg as determined by the 2nd generation vg titer assay. Of note, the 3.0×10^{14} vg/kg dose level equates to 3.5×10^{14} vg/kg based on this historical analysis.

As of protocol v9, subsequent subjects yet to be dosed were to be administered 1.3×10^{14} vg/kg AT132 as determined by the 2nd generation vg titer assay.

Under protocol v10 and beyond, no additional subjects will be dosed.

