5.1.1.29 Serum Bile Acid Assay

Serum bile acid levels are elevated in some cholestatic disorders. To better understand cholestatic tendency in XLMTM, serum bile acid levels will be measured. This assay will be performed once, any time prior to treatment with AT132, for subjects dosed in protocol v8 and beyond. As of protocol v10, the assay will also be performed following AT132 administration according to the Schedule of Events (see [Sections 5.3.1, 5.4, 5.5, and 5.6](#)). Serum bile acid levels will preferably be collected in the fasting state; however, the samples may be collected in the non-fasting state per the Investigator's discretion.

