Appendix 9: Genetics Testing

Use/Analysis of DNA

- Genetic variation may impact a subject's response to study intervention, susceptibility to, and severity and progression of disease. Variable response to study intervention may be due to genetic determinants that impact drug absorption, distribution, metabolism, and excretion; mechanism of action of the drug; disease etiology; and/or molecular subtype of the disease being treated. Therefore, where local regulations and IRB/IEC allow, a blood sample will be collected for DNA analysis from consenting subjects.
- DNA samples will be used for research related to gene therapy or XLMTM and related diseases. They may also be used to develop tests/assays, including diagnostic tests related to gene therapy and XLMTM disease. Genetic research may consist of the analysis of one or more candidate genes or the analysis of the entire genome as appropriate.
- The samples may be analyzed as part of a multistudy assessment of genetic factors involved in the response to the gene therapy or study interventions of this class to understand the study disease or related conditions.
- The results of genetic analyses may be reported in the clinical study report (CSR) or in a separate study summary or may be published in medical or scientific journals and conferences.
- The Sponsor will store the DNA samples in a secure storage space with adequate measures to protect confidentiality.
- The samples will be retained while research on AT132 is ongoing but no longer than 15 years after the final study results have been reported and then destroyed, or other period as per local requirements.

PROTOCOL AMENDMENT
SUMMARY OF CHANGES FOR PROTOCOL VERSION 12.0

Study Title: ASPIRO: A Phase 1/2/3, Randomized, Open-Label, Ascending-Dose, Delayed-Treatment Concurrent Control Clinical Study to Evaluate the Safety and Efficacy of AT132, an AAV8-Delivered Gene Therapy in X-Linked Myotubular Myopathy (XLMTM) Patients

Protocol Number: ATX-MTM-002

Protocol Versions and Dates:	1.0 (Global)	22 February 2017
	2.0 (Global)	14 June 2017
	3.0 (Global)	25 January 2018
	4.0 (Global)	21 November 2018
	5.0 (Global)	01 May 2019
	6.0 (Global)	08 October 2019
	7.0 (Global)	07 April 2020
	8.0 (Global)	16 November 2020
	9.0 (Global)	15 January 2021
	10.0 (Global)	03 February 2022
	11.0 (Global)	16 May 2023
	12.0 (Global)	17 May 2024

Amendment 12 [Substantial]

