4.2.6 Glucocorticoid Administration

Concomitant glucocorticoid administration will be summarized by AT132 dose level and overall for the SAF. Glucocorticoids will be identified by ATCr_CD = "H02AB".

The glucocorticoid administration summary will include a summary table of:

- Duration of Taper
- Total days on protocol-specified glucocorticoid dose regimen (For subjects weighing < 60 kg, the dose will be 1 mg/kg prednisolone orally daily and for subjects weighing ≥ 60 kg, the dose will be 60 mg prednisolone orally daily) prior to taper (day prior to taper start date – Day -1 date + 1),

The day of taper start for a participant is defined as the date of first glucocorticoid record in the concomitant medication dataset where (frequency)*(dose) is less than the (frequency)*(dose) value for the initial glucocorticoid record in the dataset.

A listing of all subjects' glucocorticoid administration will be provided.

Individual subject line plots of ALT x ULN, AST x ULN, Total Bilirubin x ULN, Direct Bilirubin x ULN, CK x ULN, serum bile acid x ULN, and Troponin T x ULN will be created, with a dashed vertical line indicating where the taper began.

A swimmer plot may be created to visualize the glucocorticoid administration progression.

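### Post-dose serum bile acids were scheduled only from protocol v10, after dosing had closed, so the early by-dose percentages in SAP Table 5 depend on who was tested and cannot be read as incidence

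*SAP*

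**What the plan says.** SAP 4.6.2.2 says each participant's "highest value during any post-dose follow-up visit in the following periods will be summarized by period". The periods are Baseline through Week 24, after Week 24 through Week 48, after Week 48 to end of study, and the whole study. Table 5 lists serum bile acids above 2 x ULN among the criteria. Central and local results both count. The denominator for every criterion is the number of participants with at least one value in the 24-week period, and percentages are given by treatment group.

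SAP 4.6.2.1 adds by-visit summaries and change from baseline, and names bile acids among the parameters. SAP Table 10 assigns any bile acid result from Day 1 to Day 126 to Week 12. SAP 4.2.6 plans individual line plots in which "serum bile acid x ULN, and Troponin T x ULN will be created, with a dashed vertical line indicating where the taper began".

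Protocol 5.1.1.29 sets out when the assay was scheduled. Before dosing: "This assay will be performed once, any time prior to treatment with AT132, for subjects dosed in protocol v8 and beyond". After dosing: "As of protocol v10, the assay will also be performed following AT132 administration according to the Schedule of Events". Protocol 1.4.2 states: "Under protocol v10 and beyond, no additional subjects will be dosed". The version list in the protocol's amendment summary dates v9 "15 January 2021" and v10 "03 February 2022".

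**The concern.** The other liver tests in Table 5, such as ALT, AST and bilirubin, were scheduled repeatedly for every treated child from dosing onward. Bile acids were not, but they sit in the same table with the same layout and no note that ascertainment differs. A reader will take the Baseline-Week 24 bile acid percentage as the proportion of treated children who became cholestatic by that measure, and will set low dose against high dose.

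The stakes are real. Protocol 1.5 reports serum bile acid elevations among the features of the hepatobiliary SAEs, and fatal outcomes with hepatobiliary failure in four children. The remaining purpose of the analysis (SAP 1.3) is to describe safety and efficacy at the low and high dose. A percentage whose denominator is set by the decision to test can mislead in either direction.

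**Working it through.** **Inputs**
- v10 issued 03 February 2022; v9 issued 15 January 2021; v8 issued 16 November 2020 (version list).
- High dose: 17 children dosed by the 08 July 2020 cutoff. Protocol 1.4.2 reports that "8 of 17 subjects (47.1%) experienced 26 SAEs considered related to AT132".
- Low dose: 6 children, all at least 2 years past dosing at that cutoff (Protocol 1.4.2), so dosed by 08 July 2018.
- Three controls were still undosed at v8/v9, with dosing to resume at the low dose (Protocol 3.1). Two controls were never dosed (SAP 1.3).
- Bile acid windows in SAP Table 10: Week 12 is Day 1-126, Week 24 is Day 127-210, Week 48 is Day 295-396, Month 15 is Day 397-502, Month 18 is Day 503-639.

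**Step 1. Time from dosing to v10.**
- High dose: 08 July 2020 to 03 February 2022 = 575 days (575/7 = 82.1 weeks; 1.6 years). With dosing as Day 1, this is Day 576 or later.
- First six low dose: 08 July 2018 to 03 February 2022 = 1306 days (3.6 years), so Day 1307 or later.

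These are minimums. Site adoption of v10 after its issue date would lengthen them.

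**Step 2. Compare with the windows.** Day 576 is past the end of the Week 24 window (Day 210) and of the Week 48 window (Day 396). The first window a v10-scheduled sample can reach in the high-dose group is Month 18. For 17 + 6 = 23 children, the number who can have a scheduled value in Baseline-Week 24 is 0, and in >Week 24-48 it is 0. All 23 were dosed before v8, so none had a required pre-dose sample either. SAP 4.10.1 takes baseline from this study only.

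**Step 3. The remaining child.** 3 - 2 = 1 control appears to have been dosed under v8/v9, at the low dose, on a date not given.

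| Assumed dosing date | Study day at v10 | Table 10 window |
|---|---|---|
| 16 November 2020 (v8 issue) | 445 | Month 15 |
| 15 January 2021 (v9 issue) | 385 | Week 48 |
| 09 July 2021 or later | 210 or less | Week 24 or earlier |

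The number of children who could have a scheduled value in the first 48 weeks is therefore 0 or 1 at low dose and 0 at high dose.

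**Step 4. The denominator.** In the early period the percentage is (number above 2 x ULN) / (number tested). As an illustration only, take five high-dose children above threshold. Five is the number with AT132-related hepatobiliary SAEs at the cutoff (Protocol 1.4.2); their bile acid results are not reported. If only those five were tested, the table shows 5/5 = 100%. If all 17 were tested, it shows 5/17 = 29.4%. The same clinical experience gives either figure. If unscheduled samples were instead excluded, the high-dose early cells would be empty.

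**Step 5. The late row.** Nearly all scheduled values lie after Week 48. Applied literally, the 24-week denominator counts children tested early while the numerator counts children tested years later. Those are different sets, and the ratio could exceed 100% or be undefined. If the denominator sentence is meant for the 24-week summary only, the later and overall rows have no stated denominator.

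**The case against.** The strongest reply has four parts.

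First, everything is descriptive (SAP 2 and 4.1), no dose comparison is tested, and bile acids are additional monitoring (Protocol 4.6.2). Direct bilirubin, ALP and the combined criteria in the same table cover cholestasis. This limits the damage, but a descriptive percentage by dose and period is still read as a rate.

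Second, a reader might infer that the early rows contain only off-schedule samples from children tested for cause, and that the percentage must approach 100%. The documents do not support that. One low-dose child could have scheduled values. Nothing says how many pre-v10 post-dose samples exist, in which dose group, or why they were drawn. Protocol 1.5 makes clinically driven testing plausible, but the cells could be sparse, mixed or empty.

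Third, a reader might conclude that the early and overall bile acid rows should be deleted. That would do harm. The three high-dose children with fatal events by July 2020 could never give a v10-scheduled value, so a scheduled-only table would leave them out of every bile acid cell. A worst-value safety table should keep unscheduled abnormal results. This part of the reply stands in full.

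Fourth, the taper plots are individual and estimate no rate, a child without a pre-dose value has no change from baseline to contribute, and all laboratory results are listed anyway (SAP 4.6.2.1). These points stand too. They leave the by-dose percentages and their denominator as the problem.

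**Conclusion.** The point holds for the percentages and the denominator. For 23 of about 24 dosed children, no protocol-scheduled bile acid can exist at baseline or in the first 48 weeks. The early percentages in Table 5 are conditional on having been tested, cannot be read as incidence, and cannot be compared between doses. The 24-week denominator does not fit the row that will hold nearly all the scheduled data. That row also covers only children still followed from 2022, at least 1.6 years after dosing at high dose and at least 3.6 years in the first six at low dose.

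The conclusion rests on the stated version dates and the July 2020 head counts. The total of 24 assumes that no replacement child was enrolled under v8/v9. The size of any distortion cannot be computed, because neither document gives the number or origin of the early samples. This is worth correcting in the SAP before lock, but it does not affect the other liver criteria's ascertainment or the efficacy analyses.

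**What to change.** In SAP 4.6.2.2, for serum bile acids only:
1. Use a denominator specific to each period.
2. For Baseline-Week 24, >Week 24-48 and overall, show number above 2 x ULN, number tested and number dosed, by dose and by scheduled or unscheduled sample. Give no by-dose percentages, and add a footnote that scheduled post-dose testing began with v10.
3. Give percentages only for scheduled samples in the >Week 48 period, with number tested and time since dosing by dose.

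In SAP 4.6.2.1, state that bile acid change from baseline covers only children with a pre-dose value, and show n.

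Keep unscheduled abnormal values in the table and listings, and keep the individual taper plots in SAP 4.2.6 with unscheduled points marked. Do not label pre-v10 values as clinically driven unless the source records show it.

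The cost is a few lines of SAP text, a scheduled/unscheduled flag (Protocol 5.8 already puts additional assessments on unscheduled-visit forms) and fewer bile acid percentages. No data are lost.
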